The antimuscarinic (anticholinergic) effects of belladonna alkaloid are dose dependent and include relaxation of smooth muscle, bronchodilation, pupil dilation, decreased gastric motility, transient tachycardia, and, most significant for this study, decreased tone and amplitude of ureteral and bladder contractions. B&O suppositories pair the belladonna anti-spasmodic with analgesia of an opioid to minimize discomfort associated with ureteral spasm. B&O suppositories have been used safely in robot assisted laparoscopic prostatectomy studies [15]. Administration of B&O suppositories prior to urologic procedures has been shown to decrease IV pain medication requirements and overall pain postoperatively [14]. The common B&O suppository formulation contains 16.2mg Bella Donna and 30 or 60 mg of opium and may be dosed as 1 suppository 1-4 times a day. The cost of this medication is approximately \$400 for 12 tabs.

Contraindications to this medication include hypersensitivity to belladonna, opiate, or any component of the formulation; glaucoma; severe renal or hepatic disease; bronchial asthma; respiratory depression; convulsive disorders; acute alcoholism; premature labor. Adverse reactions occur with an undefined frequency but may include palpitations, dizziness, drowsiness, pruritus, urticarial, constipation, nausea/vomiting, xerostomia, urinary retention, blurred vision, photophobia. The anti-cholinergic effect of BoNT, when therapy administration is closely monitored, is not likely since a single B&O dose will have worn off long before the 2-4 week onset period of BoNT is complete. Minimal systemic effect has been noted with suppository administration. Additionally, patients undergoing this therapy have theoretically already withstood an anticholinergic trial as a first line treatment for OAB/NB [28, 29].

Study Rationale

Data are lacking to demonstrate the ideal pain control regimen during office injections of BoNT. This is likely due to the relatively new application of this procedure in office. One study comparing average pain during intravesicle injections with use of alkalized lidocaine vs lidocaine gel demonstrated no result [13]. Additionally, it is difficult to accurately represent the patient pain experience. The Numeric Rating Scale (NRS) is a

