Confounding variables will be included in the model if point estimates change by more than 20% with their inclusion. Continuous variables will be assessed for linearity and converted to categorical variables as indicated by model fit statistics (c-statistic, Deviance, Pearson, Hosmer-Lemeshow). Cochran-Armitage and Goodness of Linear Fit tests will be used to evaluate for linear trends between suppository treatment and our primary outcome.

All statistical analyses will be two-sided. P-value of less than 0.05 is considered to be statistically significant. An interim analysis will be performed one year after Institutional Review Board if the study has not completed data collection within one year. Results will not be given to participants.

Participants

Patients will be approached for participation once they have selected BoNT therapy for treatment of overactive bladder (OAB), neurogenic detrusor overactivity (NDO), or refractory interstitial cystitis (IC).

To be included in this study, patients must be 18 years old or older at the time of the informed consent discussion, have met clinical criteria under outside care or during the Principal Investigator's routine standard of care for BoNT injection therapy (failed initial medical management), and there must be no contraindication to BoNT therapy as outlined by drug manufacturer guidelines (Table 1). Patients will have elected to have the BoNT injection therapy prior to being offer enrollment into the study for either OAB, NDO, or IC.

Patients will be excluded for pregnancy, currently nursing a baby, age less than 18 years, or anticipated geographic relocation within the first 3 months following treatment. Patients will be excluded if the patient reports an allergy to morphine, belladonna, or opiates. Patients will also be excluded if participating in another research study. Individuals unable to provide informed consent or to complete two-week follow-up bladder testing (post-void residual) or data collection will also be excluded. Prior to randomization, a data coordinator will verify eligibility and completeness of baseline data.

Participants will be withdrawn or terminated from participating in the study by a clinical investigator if they fail to undergo the BoNT injection procedure and do not reschedule before the conclusion of the study.

[figure not shown]

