Participants randomized to placebo will also receive standard analgesia as well as a rectal suppository composed of inactive base 40 minutes prior to bladder injection.

Study drug will be provided by a compounding pharmacy [REDACTED] that can produce visibly identical active and placebo suppositories. Dosage of the compounded active suppository is belladonna 16.2mg and morphine 7.5mg, which matches the commercially available belladonna and opium suppositories (belladonna 16.2mg + opium powder 60mg). Compounded belladonna dose will be the same (16.2mg) and morphine equivalent dose (7.5mg) will be used in place of powdered opium component. Using morphine, which carries a Schedule 2 narcotics classification, requires adhering to DEA restrictions for compounding purposes. The Principal Investigator will write an authentic prescription for each participant enrolled in the study (each prescription will refer to the research study, and will request "B&O suppository or placebo"), which will assist with adhering to guidelines for using Schedule 2 narcotics in clinical practice. Blinding afforded by using similar suppositories also enhances study rigor.

The B&O suppository and placebo pills participants receive will not be billed to the patient's insurance company.

Origin, Tracking, and Dispensing of Suppositories

The placebos and B&O suppositories will be purchased from [REDACTED]

The pharmacy will compound belladonna and morphine suppositories (16.2mg/7.5mg) to the same dose equivalent of opium (60 mg). Compounding the belladonna and morphine (morphine sulfate 7.5 mg is approximately equivalent to powdered opium 60 mg) would be more feasible for the study than using commercial B&O suppositories because the pharmacy cannot duplicate the exact size and shape of the commercially available B&O suppositories for research purposes. Due to the research being double-blinded to the participant and the investigators, compounded belladonna and morphine suppositories will be used. Compounded belladonna and morphine is a commonly used, and is pharmacologically equivalent to belladonna and opium suppositories.

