A sample from each batch of compounded suppositories will be sent off for third-party testing to test the suppositories for chemical validity.

Participant Timeline

The length of participation in this study will be approximately two weeks from the day of the injection procedure. Table 2 illustrates the procedures or tasks to be completed during each appointment.

Table 2. ROBIN Trial Participant Timeline	
Appointment	Task/Objective
Patient Consents to Undergo Bladder Injection Therapy	
 • Patient elects to receive BoNT therapy as standard of care treatment for overactive bladder, neurogenic detrusor overactivity, or refractory interstitial cystitis • If patient meets inclusion criteria, patient is consented and offered enrollment into the study • Participant receives a participant ID number based on sequential numbering • Principal Investigator completes prescription and sends to compounding pharmacy to fill based on participant ID number
Day Prior to Procedure	
 • If informed consent is obtained, the blinded suppository will be hand delivered to the clinic by the compounding pharmacy • The suppository will be locked in a medicinal refrigerator until time of the procedure
Day of Procedure	
 • Participant checks in for procedure, and completes pain assessment (P_0) • Principal Investigator administers the suppository or placebo to the participant • Participant completes pain assessment after receiving analgesia for the procedure (P_a) • Participant undergoes BoNT procedure and completes pain assessment (P_{10}, P_{20}) • Participant completes voiding residual trial • Adverse effects or serious events are assessed • Participant is released from clinic
2-weeks follow-up visit	
 • Participant completes voiding residual trial and adverse effects or serious events are assessed • Participant receives \$25 gift card incentive for completing the study

Risks to Subjects

Because the patient has already given consent to receive the BoNT therapy, any risks associated with the procedure while participating in this study are within normal bounds for any patient electing to undergo the procedure. Overall, the risks involving the use of the B&O suppository are comparable to not utilizing it during the BoNT therapy

procedure. Use of this particular suppository should not significantly increase or decrease risks to the patient.

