The Principal Investigator will screen potential subjects based on the inclusion and exclusion criteria. Potential subjects will have met the clinical criteria to be treated with BoNT therapy prior to screening for the study.

Informed Consent Process

Clinical visits will occur at Wichita Women's Pelvic Surgery Center at Associates in Women's Health (WWPSC) in Wichita, KS. Investigators and research staff will be available to answer patient questions at the time of the informed consent interview. The consenting process will take place after patient in-processing according to standard clinic operating protocols, and after the patient has satisfied the clinical criteria and has elected to undergo BoNT injection therapy with the Principal Investigator.

After electing to undergo the injection therapy, the Principal Investigator will review the eligibility criteria to determine if the patient is eligible to participate in the study. If all inclusion criteria are met, the Principal Investigator or a member of the research team will present the informed consent form to the patient and will discuss the study with the potential subject. The patient will be informed that participation is voluntary, and their decision to participate will not affect their medical treatment or procedures related to the BoNT injection therapy. Consent will only be sought from those patients that meet fulfill the study inclusion criteria. All materials will be provided to the patient and the conversation will take place in English (Appendix A – ROBIN Consent Form).

After all questions have been answered, and the patient has had adequate time to review the informed consent form, if the patient would like to participate, the research team will ask the participant to sign the consent form. If the patient would like additional time to review the informed consent form and to consider participation, the patient can either schedule a visit to complete the form before their visit, or can sign the informed consent form when they check in for their procedure.

A copy of the signed consent will be provided to the participant. The Principal Investigator will be notified that the patient consents to participate in the study. After consenting, the investigators and research assistant will review all materials for completeness before the subject leaves the clinic site.

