If consent to participate in the study is not given, no information collected during the visit will be used in the study. Instead, the information will be used for normal documentation of patient care.

Patients will be consenting to data collection and to research participation to receive an intervention or a placebo above and beyond standard clinical practice.

Alternatives to Participation

The alternative to participating in this study would be to not participate in the study. The patient will still undergo the BoNT therapy as anticipated. Even if the patient declines to participate in the study, the patient would still receive the B&O suppository as the Principal Investigator's standard of care, or patients can notify the clinician they do not want to utilize a suppository.

Costs to Subjects

The study subject will be responsible for costs associated with the BoNT injection therapy, and standard medical costs associated with their treatment. In the instance that the insurance company will not pay for the injection therapy or the associated standard of care procedures, the subject will be notified, and the subject will be responsible for the costs associated with their medical treatment. If the subject does not have insurance, the subject has previously agreed to cover the costs associated with the treatment.

The only costs that the subject will not be responsible for are those related to the study procedures. The subject is not required to cover the cost of the suppository, or the pain assessment forms.

New Study-Related Information

Although investigators do not anticipate developments in research or information related to the study, the study subject will receive new information from investigators via letter correspondence. Any correspondence will be disseminated by the Principal Investigator, and the data coordinator will track and monitor that each study subject receives the information.

Participation Incentive

Subjects will receive a \$25 gift card at the conclusion of the 2-week follow-up appointment to assist with travel/driver costs. If the subject withdraws before the 2-week follow-up, the participant will not receive an incentive for participation.

Research-Related Injury

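### Six of the eight contraindications that the protocol lists for the belladonna-opiate suppository have no matching eligibility rule

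*Combined protocol and SAP*

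**What the plan says.** The Background section, in its description of the suppository, gives hypersensitivity to the drug or its components as a contraindication and continues: "glaucoma; severe renal or hepatic disease; bronchial asthma; respiratory depression; convulsive disorders; acute alcoholism; premature labor".

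The Participants section sets the eligibility rules. Its one general clause on contraindications concerns the botulinum toxin: "there must be no contraindication to BoNT therapy as outlined by drug manufacturer guidelines (Table 1"). For the suppository it says: "Patients will be excluded if the patient reports an allergy to morphine, belladonna, or opiates". The remaining exclusions are pregnancy, nursing, age under 18, expected relocation, taking part in another study, and inability to consent or to complete follow-up or data collection.

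Two checks apply these rules. The text just before Informed Consent Process says: "The Principal Investigator will screen potential subjects based on the inclusion and exclusion criteria". The Participants section adds: "Prior to randomization, a data coordinator will verify eligibility and completeness of baseline data".

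A third step involves clinical judgement. Under Research Intervention, "The Principal Investigator will write an authentic prescription for each participant enrolled in the study". In Table 2 (Participant Timeline) this step follows the issue of the sequential participant number: "Principal Investigator completes prescription and sends to compounding pharmacy to fill based on participant ID number".

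On care outside the trial, Alternatives to Participation says: "Even if the patient declines to participate in the study, the patient would still receive the B&O suppository", unless the patient does not want one.

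**The concern.** Eligibility imports the contraindications of the treatment that every patient gets as routine care (BoNT), but not most of those of the drug that the trial assigns at random. The protocol itself states that certain patients should not be given the suppository, then admits those patients under its own criteria. The investigator's screening and the coordinator's verification can both be carried out faithfully and still pass such a patient, because both apply the incomplete list.

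What is at stake is patient safety. Half of those enrolled receive belladonna 16.2 mg with morphine 7.5 mg.

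A smaller consequence concerns the analysis. If the problem is noticed only when the prescription is written, the participant number is already fixed and, with it, the assigned suppository. Refusal at that point is a loss after randomisation in a 26-patient trial that plans an intent-to-treat analysis and states no allowance for dropout.

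**Working it through.** **Step 1: match each contraindication to the rules.** The inputs are the contraindication list in Background, the inclusion and exclusion criteria in Participants, and Table 1 (BoNT contraindications).

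| Entry in Background | Matching rule in Participants or Table 1 |
|---|---|
| Hypersensitivity | Yes: reported allergy to morphine, belladonna or opiates |
| Glaucoma | None |
| Severe renal or hepatic disease | None |
| Bronchial asthma | None |
| Respiratory depression | None |
| Convulsive disorders | None |
| Acute alcoholism | None by name; the consent-capacity rule might stop some intoxicated patients |
| Premature labor | Yes, indirectly: pregnancy is excluded |

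There are 8 entries, of which 2 are covered and 8 − 2 = 6 are not; 6/8 = 75%. Entries are counted as the protocol's semicolons separate them. With renal and hepatic disease counted separately, the result is 7 of 9. The count is lenient on hypersensitivity: Background includes any component of the formulation, and the allergy rule does not.

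Table 1 covers infection, toxin hypersensitivity, urinary retention and residual volume, self-catheterisation, antiplatelet and anticoagulant therapy, and antibiotic compliance. It names none of the six.

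**Step 2: does a later step close the gap?**

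- Screening and coordinator verification both use the written criteria, so they inherit the gap.
- The prescription is explained in Randomization and in Research Intervention as a means of meeting the rules for Schedule 2 drugs. No review of contraindications is attached to it.
- The discretion to remove a participant (Cessation Rules/Termination of Study) applies when study requirements are not met. Freedom from these six conditions is not a study requirement.

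**Step 3: chance of exposure, as illustration.** Randomization assigns the two groups with equal probability, and Sample size gives 13 per group, 26 in total. If k affected patients are enrolled and nobody is stopped at prescription,

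P(at least one gets active drug) = 1 − C(26 − k, 13) / C(26, 13).

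- k = 1: 1 − 13/26 = 0.50
- k = 2: 1 − (13 × 12)/(26 × 25) = 1 − 156/650 = 0.76
- k = 3: 1 − (13 × 12 × 11)/(26 × 25 × 24) = 1 − 1716/15600 = 0.89

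The documents give no figure for k. These values show only that a small number of affected patients would make exposure likely; the conclusion does not depend on them.

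**The case against.** The strongest reply is that the practical risk is small and already managed. The drug is one dose given in clinic by the investigator, followed by 40 minutes before injection. Adverse events are assessed after the suppository, during the procedure and at the voiding trial; a driver is required; and unblinding is available by telephone. Background says that systemic effect from a suppository is minimal and that these patients have in theory already tolerated an anticholinergic. The investigator who screens the patient also prescribes and administers the drug. The same investigator would normally give the suppository outside the trial, so 1:1 randomisation lowers exposure relative to that routine. Finally, 75% counts list entries and does not measure risk.

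Much of this stands as mitigation. The supervised single dose and the adverse event checks limit harm. Total exposure may well not rise. Respiratory depression and acute alcoholism are probably rare at an elective visit, so the practical gap is mainly glaucoma, asthma, convulsive disorders and severe renal or hepatic disease. Declining to prescribe would also still prevent exposure, because the prescription precedes dispensing; its place after the participant number matters for the allocation and the analysis rather than for safety.

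None of it screens anyone out. The protocol qualifies the anticholinergic argument as theoretical and applies it to overactive and neurogenic bladder, while interstitial cystitis is also enrolled. Background notes too that BoNT is indicated for adults who did not tolerate anticholinergics. Prior anticholinergic use says nothing about morphine. The remark on minimal systemic effect sits in the same paragraph as the contraindications and does not withdraw them. Routine prescribing outside the trial is an individual clinical decision; a trial needs a written rule on who may be randomised to the drug.

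**Conclusion.** The concern holds. As written, the criteria admit patients whom the protocol itself describes as contraindicated for the randomised drug: 6 of 8 listed entries have no matching rule. This should be corrected before patients are enrolled, because it is a safety gap in the eligibility rule for the study drug and is simple to close.

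The conclusion assumes that the patient meets all other criteria, and it rests on the text of Participants and Table 1. The figure that closes Participants, the appended forms and the text leading into the screening paragraph could not be read. How many affected patients would present is unknown. Which entries should be absolute exclusions for a single rectal dose is a clinical judgement that the documents do not settle.

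**What to change.** Add one exclusion to Participants: *any contraindication to the belladonna-opiate suppository as listed in the Background section*. Make it an item in the coordinator's existing verification before randomisation, using the diagnoses, past medical history and medications that Table 4 already collects. The investigator should confirm the clinical content of the list first. If any entry is judged not to apply to a single dose, the protocol should say so and give the reason.

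The cost is one line in the criteria, one item on the screening check and an amendment to the review boards. No new data are collected, and the sample size stays at 13 per group. A few candidates would become ineligible, which would slow recruitment to 26 slightly and narrow the population. Any such patient would be identified before a participant number is issued, which also avoids the post-randomisation loss.

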Eligible participants will be assigned with equal probability to one of two treatment groups: belladonna and opiate (B&O) suppository and inactive placebo suppository. Block randomization will be utilized to maintain balance between study group sizes over time and to enhance blinding of the clinical investigators; a repeated run of placebo or active suppositories may lead to an anticipatory bias effect on subsequent participants. An online randomized block generator will be utilized. Block size will be randomized and will not be revealed to clinical investigators. As the proposed study is double-blinded, selection bias is unlikely.

Study drug suppositories will be randomized in sequential pill canisters. Aside from standard indications to do otherwise, treatment allocation will remain concealed until enrollment and follow-up visits have been completed.

Working with the compounding pharmacy, an unblinded data coordinator will label, and track, the active and placebo drug assignments. Once the patient has consented to participate in the study, the Principal Investigator will assign the participant sequentially, and will notify the data coordinator and compounding pharmacy. Based on a sequential numbering system, the participant will be randomized to receive either the B&O suppository or the inactive placebo suppository based on the block assignment. The Principal Investigator will complete an authentic prescription in order to comply with all Drug Enforcement Administration (DEA) requirements for securing Schedule 2

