narcotics. The prescription will be provided to the compounding pharmacy, which will fill the prescription based on the pre-determined randomization scheme. The compounding pharmacy will document and deliver the pill canister matching the participant's ID number, to the clinic and provide it to the Principal Investigator to store in a locked medicinal refrigerator in a locked room until the day of the procedure. Prior to administering the suppository to the patient during the procedure, the Principal Investigator will open the pill canister and document the pill canister number and the number labeled on the suppository in the patient's medical record, and study documents. If unveiling the randomization for a participant is required, the Principal Investigator can call the data coordinator or the compounding pharmacy, and the coordinator or the lead pharmacist will reveal the participant's randomization assignment over the phone. Monthly meetings will be conducted to audit the enrollment and to ensure randomization procedures are conducted appropriately.

Statistical Analysis

Preoperative demographic variables including age, race, parity, body mass index (kg/m^2), menopausal status, smoking status, medical comorbidities, and indication for BoNT treatment (OAB vs. NDO) will be compared between active and placebo patients. Continuous variables will be compared using Student t-tests. Categorical variables will be described as frequency data (proportions & percentages) and compared using Chi-square or Fisher's exact test (when expected values in any cell are less than 5). Ordinal variables will be compared using Wilcoxon Rank Sum tests.

An intent-to-treat analysis approach will be used. Results for the active group versus the control group will be compared with paired t-tests if the data are normally distributed and with Mann-Whitney tests if the data are skewed. Regression modeling will be used to analyze the relationship between our primary outcome with the following predictor variables; active vs. placebo, indication for BoNT injection (OAB vs. NDO), demographic variables, and pain scores (before-during-after procedure). Interactions between variables will be assessed and, if significant, included in the model.

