The active suppositories and placebo suppositories will be compounded to be physically identical, and will be provided directly to the Principal Investigator located at Wichita Women's Pelvic Surgery Center at Associates in Women's Health, by the compounding pharmacy. The Principal Investigator will not know the identity of the suppositories. The data coordinator will maintain a master tracking list of the suppository with an inventory or ID number provided by the pharmacy as to which ID numbers are placebos and which are the B&O suppositories. The data coordinator will provide the randomization scheme to the pharmacy, who will fill each individual prescription based on the order the patient is consented into the study (using the participant's ID number), and will place the individual suppository into a blinded pill canister. The Principal Investigator will call the data coordinator and the lead pharmacist at the compounding pharmacy when a patient has consented and will undergo the procedure. The pharmacist associated with the compounding pharmacy will hand deliver the envelope to the clinic, and document the pill canister being delivered. The data coordinator will meet the pharmacist at the clinic to audit the container, and to confirm the appropriate container is provided to the Principal Investigator. The "unblinded" label containing the actual medication provided to the patient, including the patient name, date of birth, address, and phone number will be concealed in an envelope and carried separately from the pill canister, however, in order to comply with DEA guidelines, both will be hand delivered to the clinic. The envelope with the identity of the suppository will be in a secure container under lock and key, and will only be accessible to the data coordinator. The label will be stored with the participant's study records, and not revealed to the Principal Investigator.

All suppositories will be stored in a locked refrigerator that will be kept in a locked office. The temperature will be monitored regularly for quality assurance. The Principal Investigator will administer the suppository to the participant prior to the BoNT procedure, and will document in the participant's medical record and study documents which pill number was administered to the participant. The data coordinator will monitor

and monthly audit logs to ensure randomization assignments are adhered to during the course of the study.

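### The check of eligibility before randomisation falls to the unblinded role that holds the allocation list, so allocation is not concealed at that verification step

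*Combined protocol and SAP*

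**What the plan says.** The Participants section closes its eligibility criteria with this step: "Prior to randomization, a data coordinator will verify eligibility and completeness of baseline data".

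The data coordinator's other duties are set out in two sections.

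- **Randomization.** With the compounding pharmacy, "an unblinded data coordinator will label, and track, the active and placebo drug assignments". The pharmacy will "fill the prescription based on the pre-determined randomization scheme". Block sizes vary at random and are kept from the clinical investigators.
- **Origin, Tracking, and Dispensing of Suppositories.** "The data coordinator will provide the randomization scheme to the pharmacy", and prescriptions are filled "based on the order the patient is consented into the study". "The data coordinator will maintain a master tracking list of the suppository with an inventory or ID number provided by the pharmacy", showing "as to which ID numbers are placebos and which are the B&O suppositories". The coordinator also checks each container on delivery and audits the logs monthly.

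The text before and under Informed Consent Process has the Principal Investigator screen patients and review the criteria, with consent sought only from those who qualify. Under Randomization the Principal Investigator then assigns the participant in sequence and notifies the coordinator and the pharmacy. The Principal Investigator is not told what each suppository contains.

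On bias at entry, the Randomization section says: "As the proposed study is double-blinded, selection bias is unlikely".

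**The concern.** Concealment of allocation and blinding are separate protections. Blinding keeps knowledge of the treatment from affecting care and assessment after assignment. Concealment keeps knowledge of the coming assignment from affecting who enters. A trial can blind patient and operator fully and still lose concealment if someone with a say in entry can see the list.

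Here a role that can see the list is given a check before randomisation. Random block sizes protect against guessing the next assignment. They do nothing against a person who can read it.

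What is at stake is comparability of the arms at baseline. With 13 patients per arm, one patient is 1/13 = 7.7% of an arm, so even a few selective decisions could matter. The analysis could not reveal them, because a patient held back at this point never enters the data.

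**Working it through.** **1. Can the person verifying know the next assignment?**

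| Question | Answer in the protocol | Section |
|---|---|---|
| Who verifies, and when? | A data coordinator, before randomisation | Participants |
| Is that role blinded? | No | Randomization |
| Does it hold the scheme? | Yes, it gives the scheme to the pharmacy | Origin, Tracking, and Dispensing |
| Is the scheme fixed in advance? | Yes | Randomization |
| How does a patient map to it? | By order of consent | Origin, Tracking, and Dispensing |
| From whom are block sizes hidden? | Clinical investigators only | Randomization |
| Is a second, blinded coordinator described? | Not in the available text | – |

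A fixed list used in order of consent, in the hands of the person verifying, means the next assignment can be read off.

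**2. Does the order of steps remove the problem?** No. Participants puts the check before randomisation. Randomization and Table 2 have the number issued at consent, with the coordinator told afterwards. If the check precedes the number, the coordinator can know which arm comes next. If it follows, the coordinator can know that patient's own arm.

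**3. Is there room for discretion?** Some. Age, pregnancy, nursing, reported allergy and participation in another study are factual. Whether the baseline record is complete, and whether a patient can manage the two-week follow-up and data collection, call for opinion.

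**4. How large could the effect be?** The documents do not allow a calculation, so this is an illustration.

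The plan's own figure comes first. Planned means of 8 and 4.5 differ by 3.5, with SD 3, two-sided alpha 0.05 and power 0.8. The normal approximation gives n = 2 × (1.96 + 0.84)² × 3² / 3.5² = 11.5, so 12 per arm. The exact t-test calculation gives 12.57, so 13 per arm, with power 0.814. The stated 13 is reproduced.

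Now assume:
- there is no true effect, the SD is 3 and there are 13 patients per arm;
- a prognostic factor, standard normal, has correlation ρ with the pain outcome;
- a candidate for an active slot who is above the median on that factor is turned away with probability q, and the replacement faces the same check.

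The mean of the factor among those entered to active is −0.798 × q / (2 − q), where 0.798 = √(2/π). The spurious difference, active minus placebo, is 3 × ρ times that.

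| q | Factor mean | Difference, ρ = 0.3 | Difference, ρ = 0.6 |
|---|---|---|---|
| 0.10 | −0.042 | −0.04 | −0.08 |
| 0.25 | −0.114 | −0.10 | −0.21 |
| 0.50 | −0.266 | −0.24 | −0.48 |

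A simulation of 20,000 trials per setting agreed to within 0.01 points. At q = 0.50 it put the two-sided type I error at 0.053 (ρ = 0.3) and 0.069 (ρ = 0.6).

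Against the planned 3.5 points, the range runs from 0.038/3.5 = 1% to 0.48/3.5 = 14%. The values of q and ρ are assumptions, and applying SD 3 to the change score that is the primary outcome is another.

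**The case against.** The strongest reply is that entry is really decided by the Principal Investigator, who is blinded, screens, reviews the criteria and assigns the number. The coordinator only verifies, and no section gives that role authority to refuse or defer anyone. This stands, and it limits the point. A reader might infer that the recruiter knows the allocation, or that concealment fails throughout enrolment. The documents support neither. The exposure is one step, and the power to hold a patient back there is inferred from the word for the task.

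A second reply is that the indefinite article in Participants allows for a different, blinded person. That is possible. However, the Randomization section also introduces the unblinded person with an indefinite article, and the text then speaks of a single coordinator. The available text omits the page just before the screening paragraph and a figure after Participants, so the absence of a second coordinator is established only for what can be read.

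Third, little is left to exploit. Most criteria are factual, the Principal Investigator has already applied them and could notice a reversal, and monthly meetings audit enrolment. This supports a modest estimate. The meetings are not described as independent of the study team, though, and the monthly log audit is given to the same coordinator.

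Fourth, one might illustrate the harm by supposing that a patient 2 SD (6 points) above average is kept out of one arm, moving its mean by 6/13 = 0.46 points. That does not hold up. Added to the planned means, 6 points gives 10.5 or 14, which cannot occur on the usual 0 to 10 scale (the protocol does not state the range). Procedure-day pain is also not yet measured at enrolment: the first score is taken at check-in, and the suppository arrives the day before. Selection could act only through weaker predictors such as indication or history, and the primary outcome is a change in pain, not its level.

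**Conclusion.** The point holds for the verification step only. As written, the role that checks eligibility and baseline completeness before randomisation can know the coming assignment, and the protocol's appeal to double-blinding does not answer that. This rests on reading the coordinator as one role, which is how the available text treats it.

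The illustrative range of about 0.04 to 0.48 points depends wholly on the assumed refusal rates and correlations; the upper end needs half of the poorer-prognosis candidates for one arm to be turned away. A reader might infer that the trial's result is likely to be materially biased, or that misconduct is expected. Nothing in the documents supports either. The case for change is that this is an avoidable weakness in a 26-patient trial and is cheap to remove. The sample size is unaffected.

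**What to change.** Reword the sentence in Participants so that the Principal Investigator, who is blinded and already reviews eligibility, signs and dates both eligibility and completeness of the baseline record before the data coordinator or the pharmacy is contacted. Make the order of steps in Randomization and Table 2 agree with this.

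State that the data coordinator only assigns and tracks canisters and may not accept, defer or reject a patient. Keep a log of patients who consent but are not randomised, with reasons.

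The Principal Investigator is a safer choice than the research assistant, whose blinding status is not stated. If a separate blinded coordinator was intended all along, a sentence naming that role and barring it from the list would serve equally well.

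The cost is a sentence or two, one signature line and a short log, with existing staff and no extra visits. The drawback is losing the coordinator's second check on eligibility.
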